14.3.29 Data handling and programming rules

The following section should be used as guidance for development of the protocol, data handling procedures or programming requirements (e.g. on incomplete dates).

14.3.30 Study/project specific decisions

For each study (or project) various issues need to be addressed and specified in the protocol or RAP documentation. Any deviations from protocol must be discussed and defined at the latest in the RAP documentation.

The proposed primary analysis and potential sensitivity analyses should be discussed and agreed with the health authorities and documented in the protocol (or at the latest in the RAP documentation before database lock).

14.3.31 End of treatment phase completion

Patients **may** voluntarily withdraw from the study treatment or may be taken off the study treatment at the discretion of the investigator at any time. For patients who are lost to follow-up, the investigator or designee should show "due diligence" by documenting in the source documents steps taken to contact the patient, e.g. dates of telephone calls, registered letters, etc.

The end of treatment visit and its associated assessments should occur within 14 days of the last study treatment.

Patients may discontinue study treatment for any of the following reasons:

- Adverse event(s)
- Lost to follow-up
- Physician decision
- Pregnancy
- Protocol deviation
- Technical problems
- Subject/guardian decision
- Death
- Progressive disease
- Study terminated by the sponsor
- Non-compliant with study treatment
- No longer requires treatment

14.3.32 End of post-treatment follow-up (study phase completion)

End of post-treatment follow-up visit will be completed after discontinuation of study treatment and post-treatment evaluations but prior to collecting survival follow-up.

Patients may provide study phase completion information for one of the following reasons:

- Adverse event
- Lost to follow-up

- Physician decision
- Pregnancy
- Protocol deviation
- Technical problems
- Subject/guardian decision
- Death
- Progressive disease
- Study terminated by the sponsor

14.3.33 Medical validation of programmed overall lesion response

In order to be as objective as possible the RECIST programmed calculated response assessment is very strict regarding measurement methods (i.e. any assessment with more or less sensitive method than the one used to assess the lesion at baseline is considered UNK) and not available evaluations (i.e. if any target or non-target lesion was not evaluated the whole overall lesion response is UNK unless remaining lesions qualified for PD). This contrasts with the slightly more flexible guidance given to local investigators (and to the central reviewers) to use expert judgment in determining response in these type of situations, and therefore as a consequence discrepancies between the different sources of response assessment often arise. To ensure the quality of response assessments from the local site and/or the central reviewer, the responses may be re-evaluated by clinicians (based on local investigator data recorded in eCRF or based on central reviewer data entered in the database) at Novartis or external experts. In addition, data review reports will be available to identify assessments for which the investigators' or central reader's opinion does not match the programmed calculated response based on RECIST criteria. This may be queried for clarification. However, the investigator or central reader's response assessment will never be overruled.

If Novartis elect to invalidate an overall lesion response as evaluated by the investigator or central reader upon internal or external review of the data, the calculated overall lesion response at that specific assessment is to be kept in a dataset. This must be clearly documented in the RAP documentation and agreed before database lock. This dataset should be created and stored as part of the 'raw' data.

Any discontinuation due to 'Disease progression' without documentation of progression by RECIST criteria should be carefully reviewed. Only patients with documented deterioration of symptoms indicative of progression of disease should have this reason for discontinuation of treatment or study evaluation.

14.3.34 Programming rules

The following should be used for programming of efficacy results:

14.3.35 Calculation of 'time to event' variables

Time to event = end date - start date + 1 (in days)

When no post-baseline tumor assessments are available, the date of randomization/start of treatment will be used as end date (duration = 1 day) when time is to be censored at last tumor assessment, i.e. time to event variables can never be negative.

14.3.36 Incomplete assessment dates

All investigation dates (e.g. X-ray, CT scan) must be completed with day, month and year.

If one or more investigation dates are incomplete but other investigation dates are available, this/these incomplete date(s) are not considered for calculation of the assessment date (and assessment date is calculated as outlined in [Section 14.3.26](#)). If all measurement dates have no day recorded, the 1st of the month is used.

If the month is not completed, for any of the investigations, the respective assessment will be considered to be at the date which is exactly between previous and following assessment. If a previous and following assessment is not available, this assessment will not be used for any calculation.

14.3.37 Incomplete dates for last known date patient alive or death

All dates must be completed with day, month and year. If the day is missing, the 15th of the month will be used for incomplete death dates or dates of last contact.

14.3.38 Non-target lesion response

If no non-target lesions are identified at baseline (and therefore not followed throughout the study), the non-target lesion response at each assessment will be considered ‘not applicable (NA)’.

14.3.39 Study/project specific programming

The standard analysis programs need to be adapted for each study/project.

14.3.40 Censoring reason

In order to summarize the various reasons for censoring, the following categories will be calculated for each time to event variable based on the treatment completion page, the study evaluation completion page and the survival page.

For survival the following censoring reasons are possible:

- Alive
- Lost to follow-up

For PFS and TTP [REDACTED] the following censoring reasons are possible:

- Ongoing without event
- Lost to follow-up
- Withdraw consent
- Adequate assessment no longer available*
- Event documented after two or more missing tumor assessments (optional, see [Table 14-9](#))

- Death due to reason other than underlying cancer (*only used for TTP* [REDACTED]
[REDACTED])
- Initiation of new anti-cancer therapy

*Adequate assessment is defined in [Section 14.3.26](#). This reason is applicable when adequate evaluations are missing for a specified period prior to data cut-off (or prior to any other censoring reason) corresponding to the unavailability of two or more planned tumor assessments prior to the cut-off date. The following clarifications concerning this reason should also be noted:

- This may be when there has been a definite decision to stop evaluation (e.g. reason="Sponsor decision" on study evaluation completion page), when patients are not followed for progression after treatment completion or when only UNK assessments are available just prior to data cut-off).
- The reason "Adequate assessment no longer available" also prevails in situations when another censoring reason (e.g. withdrawal of consent, loss to follow-up or alternative anti-cancer therapy) has occurred more than the specified period following the last adequate assessment.
- This reason will also be used to censor in case of no baseline assessment.

- Perform baseline clinical/laboratory studies according to the trial protocol (e.g. one could rule out carrier state of *Salmonella* spp., *Clostridium difficile*, *Campylobacter* spp., *Giardia*, *Entamoeba*, *Cryptosporidium* which can lead to opportunistic infections in immunosuppressed patients);
- Explain the frequency of diarrhea and its relationship to NCI CTCAE grading (Table 14-10).

Table 14-10 NCI CTCAE version 4.03 grading of diarrhea for patients without colostomy

Toxicity	0	1	2	3	4
Diarrhea	None	Increase of < 4 stools per day over baseline	Increase of 4-6 stools per day over baseline	Increase of ≥ 7 stools per day over baseline; incontinence; hospitalization indicated; limiting self-care ADL	Life-threatening consequences; urgent intervention indicated

Diarrhea is defined as: A disorder characterized by frequent and watery bowel movements.

First report of diarrhea

- Obtain history of onset and duration of diarrhea
- Description of number of stools and stool composition (e.g. watery, blood, mucus in stool)
- Assess patient for fever, abdominal pain, cramps, distension, bloating, nausea, vomiting, dizziness, weakness (i.e., rule out risk for sepsis, bowel obstruction, dehydration)
- Obtain medication profile (i.e., to identify any diarrheogenic agents) and dietary profile (i.e., to identify diarrhea-enhancing foods)

Proactively look for occurrence of diarrhea. If no problems occur, instruct the patient to call when a problem does arise.

Management of diarrhea

General recommendations:

- Stop all lactose-containing products, alcohol
- Stop laxatives, bulk fiber (e.g. Metamucil®) and stool softeners (e.g. docusate sodium, Colace®)
- Stop high-osmolar food supplements such as Ensure Plus® and Jevity Plus® (with fiber)
- Drink 8 to 10 large glasses of clear liquids per day (e.g. water, Pedialyte®, Gatorade®, broth)
- Eat frequent small meals (e.g. bananas, rice, apple sauce, toast)

It is recommended that patients are provided with loperamide tablets at the start of each cycle. Patients should be instructed on the use of loperamide at Cycle 1 in order to manage signs or symptoms of diarrhea at home. Patients should be instructed to start oral loperamide (initial administration of 4 mg, then 2 mg every 4 hrs (maximum of 16 mg/day) at the first sign of loose stool or symptoms of abdominal pain. These instructions should be provided at each cycle and the site should ensure that the patient understands the instruction. At the beginning of each cycle, each patient should be specifically questioned regarding any experience of diarrhea or diarrhea related symptoms. If symptoms were experienced, then the site should question the patient regarding the actions taken for these symptoms.

Intensive management of diarrhea must be instituted at the first sign of abdominal cramping, loose stools or overt diarrhea. Note that all concomitant therapies used for treatment of diarrhea must be recorded on the Concomitant Medications/Non-drug Therapies eCRF.

Loperamide is the first-line treatment of diarrhea (any Grade) in this recommended algorithm. Persistent symptoms may require the administration of high dose loperamide followed by treatment with second-line agents such as opium tincture and octreotide acetate, based on severity and duration of diarrhea and related signs/symptoms. Another first-line treatment for diarrhea is diphenoxylate hydrochloride/atropine sulfate. This medication may be used in place of loperamide however it is important to note that loperamide and diphenoxylate hydrochloride/atropine sulfate must not be used in conjunction with one another due to the risk of developing paralytic ileus. Upon treatment with any antidiarrheal agents, the patient's response to treatment should be observed and appropriately documented in the source document and eCRF.

Treatment of diarrhea CTCAE grade 1 or 2

Diarrhea CTCAE grade 1 or 2 will be treated with standard loperamide (initial at first administration 4 mg, then 2 mg every 4 hrs (maximum of 16 mg/day) or after each unformed stool).

Diarrhea resolved

- Continue instructions for dietary modification
- Gradually add solid foods to diet
- Discontinue loperamide after 12 hrs diarrhea-free interval

Diarrhea unresolved

Persisting diarrhea CTCAE grade 1 or 2 will be treated with addition of opium tincture or dihydrocodeine tartrate tablets/injections with monitoring of patients condition to rule out dehydration, sepsis, ileus) medical check and selected workup if patient does not need hospitalization (see section Diarrhea workup and additional test in the particular trial protocol). Observe patient for response to antidiarrheal treatment.

Persisting diarrhea CTCAE grade 3 or 4 may be treated with hospitalization, high dose loperamide (initial 4 mg, then 2 mg every 2 hrs) and addition of opium tincture (DTO) or dihydrocodeine tartrate tablets/injections, start of IV fluids and antibiotics as needed with monitoring of patients condition (to rule out dehydration, sepsis, ileus) medical check and workup (perform appropriate additional testing). Observe patient for response.

After again 12-24 hrs:**Diarrhea resolved**

- Continue instructions for dietary modification
- Gradually add solid foods to diet
- Discontinue loperamide and/or other treatment after 12 hrs diarrhea-free interval

Diarrhea unresolved

- If diarrhea still persisting (CTCAE grades 1 and 2), after 2x 24 hrs with high dose loperamide and opiates then admit to hospital and employ measures as for CTCAE grade 3 and 4 until diarrhea resolved.
- If diarrhea still persisting and progressed to CTCAE grades 3 and 4, employ measures described below.

Treatment of diarrhea CTCAE grade 3 or 4

Severe diarrhea CTCAE grade 3 or 4 may be treated with hospitalization, high dose loperamide (initial 4 mg, then 2 mg every 2 hrs and addition of opium tincture or dihydrocodeine tartrate tablets/injections, start of IV fluids and antibiotics as needed with monitoring of patients condition (to rule out dehydration, sepsis, ileus) medical check and workup (see section Diarrhea workup and additional test in the particular trial protocol). Observe patient for response.

After 12-24 hrs:

- If diarrhea persisting administer s.c. Sandostatin/octreotide (100-500 µg tid)
- Continue IV fluids and antibiotics as needed
- If diarrhea CTCAE grade 3 or 4 still persists patients should receive opium tincture or dihydrocodeine tartrate injections s.c. or i.m.
- If diarrhea CTCAE grade 3 or 4 is still persisting s.c. Sandostatin/octreotide (500-1000 µg TID) should be administered.
- To control and/or resolve diarrhea, next cycle of treatment should be delayed by 1 or 2 weeks. Treatment should be continued only when diarrhea resolved.

Diarrhea workup

Perform appropriate tests ([Fine et al 1999](#)).

Spot stool analysis

- Collect stool separating it from urine (special containers, analysis immediately, exceptionally freeze samples)
- Blood
- Fecal leukocytes (Wright's staining and microscopy) or
- Clostridium difficile toxin
- Fecal cultures including *Salmonella* spp., *Campylobacter* spp., *Giardia*, *Entamoeba*, *Cryptosporidium* (which can lead to opportunistic infections in immunosuppressed patients), plus *Shigella* and pathogenic *E. coli* - enterotoxigenic, enterohemorrhagic etc., possibly *Aeromonas*, *Pleisiomonas* (if suspected exposure to contaminated water)

Endoscopic examinations

Endoscopic examinations may be considered **only if absolutely necessary**. The bowel is likely to be fragile with evidence of colitis and thus great care and caution must be exercised in undertaking these invasive procedures.

- Gastroscopy to obtain jejunal fluid - re. bacterial overgrowth for cultures and biopsy of proximal jejunum to assess extent of inflammatory jejunitis
- Sigmoidoscopy - reassessment of colitis

14.5 Appendix 5 - Guidelines for the treatment of study drug induced stomatitis/oral mucositis

General guidance and management include patient awareness and early intervention. Evaluation for herpes virus or fungal infection should be considered.

Patients should be informed about the possibility of developing mouth ulcers/oral mucositis and instructed to report promptly any signs or symptoms to their physician,

Patients should be educated about good oral hygiene, instructed to avoid spicy/acidic/salty foods, and should follow the following guidelines:

- For mild toxicity (grade 1), use conservative measures such as non-alcoholic mouth wash or salt water (0.9%) mouth wash several times a day until resolution.
- For more severe toxicity (grade 2 in which case patients have pain but are able to maintain adequate oral alimentation, or grade 3 in which case patients cannot maintain adequate oral alimentation), the suggested treatments are topical analgesic mouth treatments (i.e., local anesthetics such as benzocaine, butyl aminobenzoate, tetracaine hydrochloride, menthol, or phenol) with or without topical corticosteroids, such as triamcinolone oral paste 0.1% (Kenalog in Orabase®).
- Agents containing alcohol, hydrogen peroxide, iodine, and thyme derivatives may tend to worsen mouth ulcers. It is preferable to avoid these agents.

Antifungal agents should be avoided unless a fungal infection is diagnosed as they may interfere with alpelisib metabolism (see [Section 6.4](#) and [Appendix 1](#)).

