6.1.2 Guidelines for continuation of treatment

For guidelines for continuation of treatment, refer to [Section 6.3](#) Dosing modifications.

Patients who permanently discontinue one of the study drugs for any reason other than disease progression may continue the other study drug as part of the trial therapy at the investigators discretion until disease progression, unacceptable toxicity, death or discontinuation from study treatment due to any other reason and should follow the protocol safety and efficacy assessments as scheduled. After discontinuing all study treatment, further treatment is left to the physician's discretion.

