6.3.1.2 Alpelisib/placebo

Management of severe or intolerable adverse reactions requires dose reduction, temporary interruption, and/or discontinuation of alpelisib therapy. A maximum of 2 dose reductions will be allowed, after which the patient will be discontinued from treatment with alpelisib/placebo. Dose reduction should be based on the worst preceding toxicity.

Please refer to [Table 6-2](#) and [Table 6-3](#) for guidance.

Table 6-2 Dose reduction sequential steps for alpelisib/placebo

Alpelisib/placebo dose level	Dose and schedule	Number of tablets & strength
Starting dose	300 mg/day continuously	1 x 200 mg tablet and 2 x 50 mg tablet
Dose level -1	250 mg/day continuously	1 x 200 mg tablet and 1 x 50 mg tablet
Dose level -2	200 mg/day continuously	1 x 200 mg tablet

Recommendations for dose reduction or dose interruption of alpelisib/placebo in the management of adverse reactions are summarized in [Table 6-3](#). No dose modification for fulvestrant is permitted. Clinical judgment of the treating physician, including confirmation of lab values if deemed necessary, should guide the management plan of each patient based on individual benefit/risk assessment.

However, treatment must be discontinued as indicated in [Table 6-3](#).

After treatment is resumed at a lower dose:

- If the same toxicity recurs with the same severity, then the next treatment re-initiation must resume at a lower dose irrespective of duration.
- Once the alpelisib/placebo dose has been reduced, no re-escalation will occur, even upon resolution of AE.

If a patient requires a dose delay of alpelisib/placebo for > 28 days from the intended day then the patient must be discontinued from alpelisib/placebo, but may continue on fulvestrant. All scheduled assessments will continue to be performed. If fulvestrant is held for more than 35 days since a planned injection, then fulvestrant should be permanently discontinued. The patient may continue on alpelisib/placebo at the discretion of the investigator until study completion, in which case all scheduled assessments will continue to be performed.

Table 6-3 Criteria for interruption and re-initiation of alpelisib/placebo treatment

Dose Modifications for alpelisib/placebo as specified below. Fulvestrant may be continued while alpelisib/placebo dose is being held, at the investigators discretion, and as specified in Section 6.3.1	
Worst toxicity -CTCAE Grade (value)	Dose Modifications for alpelisib/placebo

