Cardiac - Left Ventricular Systolic Dysfunction	
Asymptomatic, resting ejection fraction 40-50%; or 10-20% drop from baseline	
 -Maintain dose level, and continue alpelisib with caution -Repeat LVEF within 4 weeks or as clinically appropriate
Symptomatic, responsive to intervention, ejection fraction 20-39% or > 20% drop from baseline	
 -Omit alpelisib/placebo until resolved* (as defined below), then \downarrow 1 dose level -LVEF measurement to be repeated, if not resolved* within 28 days permanently discontinue patient from alpelisib/placebo treatment
Refractory or poorly controlled, ejection fraction < 20%	Permanently discontinue patient from alpelisib/placebo
<small>*the event is considered resolved when the patient is asymptomatic, has a resting ejection fraction \geq 40% and \leq 20% decrease from baseline.</small>	

Dose Modifications for alpelisib/placebo as specified below. Fulvestrant may be continued while alpelisib/placebo dose is being held, at the investigators discretion, and as specified in Section 6.3.1	
Worst toxicity -CTCAE Grade (value)	Dose Modifications for alpelisib/placebo
Other Cardiac Events	
Grade 1 or 2	Maintain dose level
Grade 3	Omit dose until resolved to \leq Grade 1, then \downarrow 1 dose level
Grade 4	Permanently discontinue patient from alpelisib/placebo
Investigations (Gastrointestinal)	
Diarrhea (see also Appendix 4)	
Grade 1	Maintain dose level but initiate appropriate medical therapy and monitor as clinically indicated
Grade 2	Omit dose until resolved to \leq Grade 1, then restart at same dose If diarrhea returns as \geq Grade 2, then omit dose until resolved to \leq Grade 1, then decrease 1 dose level
Grade 3	Omit dose until resolved to \leq Grade 1, then \downarrow 1 dose level Manage according to local standard of care medical management, including electrolyte monitoring, administration of antiemetics and antidiarrhoeal medicinal products and/or fluid replacement and electrolyte supplements, as clinically indicated
Grade 4	Discontinue patient from treatment. Manage according to local standard of care medical management, including electrolyte monitoring, administration of antiemetics and antidiarrhoeal medicinal products and/or fluid replacement and electrolyte supplements, as clinically indicated.
Investigations (Pancreatic)	
Pancreatitis	

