7.1.3 Discontinuation of study treatment

Patients may voluntarily discontinue from alpelisib/placebo and/or fulvestrant for any reason at any time. If a patient decides to discontinue from the study treatment, the investigator must make every effort (e.g. telephone, e-mail, letter) to determine the primary reason for this decision and record this information in the patient's chart and on the appropriate CRF pages. They may be considered withdrawn if they state an intention to withdraw, fail to return for visits, or become lost to follow-up for any other reason.

The investigator should discontinue alpelisib/placebo and/or fulvestrant for a given patient if, she/he believes that continuation would be detrimental to the patient's well-being.

For patients who discontinue treatment for reasons other than documented disease progression, death, lost to follow-up, or withdrawal of consent, tumor assessments must continue to be performed every 8 weeks during the first 18 months, every 12 weeks until 36 months, then as clinically indicated until documented disease progression, death, lost to follow-up, or withdrawal of consent.

Study treatment must be discontinued under the following circumstances:

- Adverse event or laboratory abnormalities as indicated in [Section 6.3](#).
- Pregnancy
- Lost to follow-up
- Physician decision
- Subject/guardian decision
- Death
- Progressive Disease
- Study terminated by sponsor
- Technical problems
- Use of prohibited treatment and medications refer to [Section 6.4.3](#) and [Section 14.2](#).
- Any other protocol deviation that results in a significant risk to the patient's safety

The appropriate personnel from the site and Novartis will assess whether alpelisib/placebo plus fulvestrant treatment should be discontinued for any patient whose treatment code has been broken inadvertently for any reason.

Patients who discontinue only one of two medications (fulvestrant or alpelisib/placebo) should NOT be considered withdrawn from the study. They should continue taking fulvestrant only or alpelisib/placebo only (as applicable) as per investigators' clinical judgment, and return for the assessments indicated in [Table 7-1](#).

If they fail to return for these assessments for unknown reasons, every effort (e.g. telephone, email, letter) should be made to contact them as specified in [Section 7.1.8](#).

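### For Grade 4 diarrhea, Appendix 4 provides for a delay and conditional continuation, while Table 6-3 requires discontinuation

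*Protocol*

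**What the plan says.** Two current parts of the protocol tell a site what to do with treatment in severe diarrhea.

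- **Table 6-3 (Section 6.3.1.2)** separates the grades. At Grade 3 the dose is omitted until recovery to Grade 1 or lower and then stepped down by "1 dose level Manage according to local standard of care medical management". At Grade 4 the row reads "Discontinue patient from treatment. Manage according to local standard of care medical management". The row heading sends the reader on: "Diarrhea (see also Appendix 4)".
- **Appendix 4 (Section 14.4)**, under a single heading for CTCAE grade 3 or 4, closes with a bullet stating that the "next cycle of treatment should be delayed by 1 or 2 weeks. Treatment should be continued only when diarrhea resolved". It does not split the grades, mention a dose level, or say that Table 6-3 takes precedence.

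Three other places bear on which text governs. Section 6.1.2 opens "For guidelines for continuation of treatment, refer to" Section 6.3. Section 7.1.3 lists, among the reasons for which study treatment must stop, "Adverse event or laboratory abnormalities as indicated in" Section 6.3. Section 6.3.1.2 presents reductions and interruptions as recommendations subject to clinical judgment, then adds "However, treatment must be discontinued as indicated in" Table 6-3.

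**The concern.** A site that follows the cross-reference from Table 6-3 to Appendix 4 meets a second instruction about study treatment. For Grade 4 that instruction differs from the one it has just left. Table 14-10, inside Appendix 4, defines Grade 4 diarrhea as life-threatening, so this is a safety instruction that ought to read the same wherever it appears. At stake is whether a patient with Grade 4 diarrhea might be held for a week or two and then re-exposed to alpelisib/placebo, when Table 6-3 stops the drug.

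**Working it through.** The plan gives no figure to reproduce here; the check is a comparison of texts.

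| Situation | Table 6-3 | Appendix 4, last bullet | Relation |
|---|---|---|---|
| Grade 3, hold | Omit until Grade 1 or lower | Delay 1 or 2 weeks; resolution required before going on | Compatible |
| Grade 3, dose on restart | One level lower | Not stated | Silence |
| Grade 4 | Discontinue; no restart rule given | Same text as for Grade 3 | Conflict |

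**Grade 4.** The bullet has two sentences, and they carry different weight. The second makes resolution a necessary condition for continuing. Taken alone, it is not breached by a patient who never continues. The first recommends a delay of finite length, 1 or 2 weeks, to the next cycle. A finite delay has meaning only if a next cycle follows. Table 6-3 marks temporary holds by telling the site to omit the dose and by giving the conditions for restart. Its Grade 4 diarrhea row does neither; it discontinues. The conflict therefore rests on the first sentence and the shared heading, and it remains even when the second sentence is read narrowly.

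**Grade 3.** Both texts hold treatment first. The bullet omits the step down, but it does not say that the same dose should be resumed. The length of the delay also fits the rules: 7 to 14 days is within the 28 days beyond which Section 6.3.1.2 requires alpelisib/placebo to be stopped.

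**Which text governs.** Sections 6.1.2 and 7.1.3 point to Section 6.3. Section 6.3.1.2 makes the Table 6-3 discontinuations mandatory. The introduction to Appendix 4 describes its content as a recommended algorithm. The appendix is the text to correct.

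**How often it could matter.** Table 1-2 gives treatment-related diarrhea in the phase I combination of alpelisib and fulvestrant, with Grades 3 and 4 pooled:

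- all doses: 2/84 = 2.4%
- 400 mg: 2/66 = 3.0%
- 350 mg: 0/8
- 300 mg, the starting dose in this trial: 0/9

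Grade 4 alone cannot exceed the pooled count, so it is at most 2 of 84 in those data. The 0/9 is weak evidence on its own. The one-sided 95% upper limit is 1 − 0.05^(1/9) = 1 − 0.717 = 28.3%.

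**The case against.** The strongest reply is that the protocol already resolves the matter. The table's stop rule is mandatory, the appendix is advisory, and the cross-reference to Appendix 4 heads the same block of Table 6-3 that contains the Grade 4 row. A site arriving by that route has the stop rule in front of it. This stands, and it is why the effect is small. It does not make the two instructions agree, and Appendix 4 says nothing about precedence.

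A second reply is that the bullet never names alpelisib. Section 6.1.2 says "Patients who permanently discontinue one of the study drugs for any reason other than disease progression may continue the other study drug", so a Grade 4 patient who is off alpelisib may still have a next cycle of fulvestrant. That reading is available but strained. The introduction to Appendix 4 concerns diarrhea induced by alpelisib, and Table 6-3 lets fulvestrant go on while alpelisib/placebo is held. Nothing in Section 6.3 calls for delaying fulvestrant because of diarrhea.

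A reader might also infer more than the texts support:

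- *That the appendix orders alpelisib to be resumed once diarrhea resolves.* It sets a condition on continuing and stops short of ordering it.
- *That Grade 3 is contradicted as well.* It is not; the bullet is silent on dose, and Section 6.3.1.2 calls the reductions recommendations.
- *That the dose steps of 300 to 250 mg and 250 to 200 mg measure the error.* They are undisputed entries in Table 6-2.
- *That delaying a cycle is incompatible with continuous dosing.* Section 6.1.1.1 describes the default schedule, and Section 6.3.1.2 allows dose delays.
- *That the bullet is text carried over from elsewhere.* The reference to a particular trial protocol is suggestive, but the workup section it points to does exist in Appendix 4. The documents do not settle where the wording came from.

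**Conclusion.** The point holds for Grade 4 only. The last bullet on grade 3 or 4 diarrhea in Appendix 4 provides for a delay and conditional continuation where Table 6-3 discontinues the patient and Section 6.3.1.2 makes that mandatory. It is an internal inconsistency in a safety instruction and should be corrected.

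The size is small. Section 6.3 governs, and the only rate in the documents is 2 of 84 for Grades 3 and 4 pooled, with 0 of 9 at 300 mg. No Grade 4 rate is given, so the number of patients affected in this trial cannot be estimated. Type I error, power and the analyses do not change.

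The conclusion assumes that the next cycle in the bullet includes alpelisib/placebo and that discontinuation in the Grade 4 row is final. The row does not use the word permanently, whereas the Grade 4 stomatitis row does. The absence of any restart rule, set against the restart rules for the lower grades, supports reading it as final.

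**What to change.** Replace the last bullet under the grade 3 or 4 heading in Appendix 4 with:

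> Alpelisib/placebo interruption, dose reduction and discontinuation follow Section 6.3.1.2 and Table 6-3: at Grade 3, omit until Grade 1 or less, then resume one dose level lower; at Grade 4, discontinue alpelisib/placebo and do not restart.

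This applies the rules of Table 6-3, makes the finality of the Grade 4 stop explicit, and leaves fulvestrant to Section 6.1.2. If the sponsor would rather not state the rules in two places, a bare pointer to Table 6-3 would also do, provided that the text on delay and continuation is removed.

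The cost is one bullet in the next amendment. Data collection, sample size and analysis are unchanged.
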